#### **4.5 Secondary Endpoint**

- 1.) KOOS-QOL subscale at pre-intervention
- 2.) KOOS-QOL subscale at post-intervention
- 3.) Daily step promotion intervention retention: percentage of patients retained at post-intervention visit
- 4.) Daily step promotion intervention compliance: percentage of days participant is compliant with fitbit monitor wear (>1,000 steps per day)

#### **4.6 Statistical Methods**

Owing to the preliminary nature and small sample size, we will emphasize estimation of effect sizes rather than formal inferential statistical hypothesis testing for future grant proposals. Pretest and posttest outcomes will be analyzed with pooled Cohen's  $d$  effect sizes and corresponding 95% confidence intervals to determine the magnitude of outcome differences between time points. The relationship between outcome changes will be analyzed using bivariate Pearson product moment

correlation coefficients and 95% confidence intervals will be constructed using Fisher's transformations to estimate the strength of the associations.

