- (2) Baseline: The second visit will include Fitbit and smartphone initialization, collection of patient reported outcomes and MRI scan of their knee. Participants will wear the fitbit monitor on their non-dominant wrist for 2 weeks during all waking hours in free-living settings in preparation for the intervention.
- (3) Intervention/Treatment: Between the second and third visit, participants will receive daily short message service (SMS) message with daily step count goals on their smart phone for 8 weeks. The daily step goal is based on an adaptive step goal paradigm in which their daily goal is based on the top 60th percentile of steps over the last 10 days.
- (4) Follow up: The third visit will include the completion of surveys, returning the fitbit monitor, instructional use of the actigraph monitor for second wear period over 7 days, and MRI.
- 

Efficacy Evaluations	
Cartilage Composition: Cartilage composition (i.e. proteoglycan density) will be measured using T1ρ relaxation times (millisecond; [ms]) of medial and lateral tibiofemoral articular cartilage from MRI imaging.
 
Daily Steps: Objective daily step counts measured via Triaxial accelerometer and averaged over 7 days or wear
 
Self-Reported Knee Function: Knee-related quality of life assessed via the KOOS-QOL questionnaire.
 
Feasibility Outcomes: intervention retention rates (%) and intervention compliance (%)

Pharmacokinetic Evaluations	N/A
Safety Evaluations	Medical Monitor & IRB, Routine Safety Reports, Expedited Safety Reports
Statistical And Analytic Plan	Estimation of effect sizes for pretest and posttest MRI measures of proteoglycan density (i.e., cartilage composition) changes will be analyzed with pooled Cohen's d effect sizes and corresponding 95% confidence intervals to determine the magnitude of outcome differences between time points. The relationship between daily step changes and MRI measures of proteoglycan density (i.e., cartilage composition) changes will be analyzed using bivariate Pearson product moment correlation coefficients and 95% confidence intervals will be constructed using Fisher's transformations to estimate the strength of the associations.
DATA AND SAFETY MONITORING PLAN	
Data tracking, entry, editing, updating and reporting will be completed by study investigators.
 
All data quality control will be performed by the Principal Investigator (PI).

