### 1.5 Secondary Objective

Aim 3. Determine the change in self-reported knee function after 8-weeks of daily step promotion. Hypothesis: Self-reported knee function measured via the Knee Injury and Osteoarthritis Outcome Score Quality of Life Subscale will increase from pretest to posttest indicating improved knee related quality of life

Aim 4: Determine intervention retention and compliance. Hypothesis: Participants will demonstrate  $\geq 90\%$  retention and  $\geq 95\%$  compliance with monitor wear.

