#### 4.7 Sample Size and Power

We will enroll 10 individuals allowing for 18% attrition (n=2 individuals not completing the study) for a total of 8 participants. With 8 ACLR individuals at each time point, we will be powered (80% power, two-tailed alpha level of 0.05) to detect a strong time effect in proteoglycan density ( $d=1.2$ ) and strong correlation ( $r=0.77$ ) between change in steps and change in proteoglycan density.

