#### 4.8 Interim Analysis

We are only collecting 8-10 participants as a proof-of-concept study for pilot data to support grant applications for larger clinical trials. Therefore, an interim analysis is not necessary.

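### Uncorrected pooled Cohen's d, planned on 8 to 10 people, is biased away from zero by about 6-11% on average at n=8; report Hedges' g instead

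*Combined protocol and SAP*

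**What the plan says.** Section 4.6 (Statistical Methods) puts estimation ahead of testing and gives the purpose: "we will emphasize estimation of effect sizes rather than formal inferential statistical hypothesis testing for future grant proposals". The estimator follows: "Pretest and posttest outcomes will be analyzed with pooled Cohen's" d, with 95% confidence intervals. As worded this covers every outcome measured before and after the intervention, so it takes in the T1rho regions of Aim 1 and KOOS-QOL under Aim 3 (section 1.5: "Determine the change in self-reported knee function after 8-weeks of daily step promotion"). The synopsis, under Statistical And Analytic Plan, says the same of the MRI measures, which "will be analyzed with pooled Cohen's d effect sizes and corresponding 95% confidence intervals to determine the magnitude of outcome differences between time points".

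Section 4.7 sets the numbers: "We will enroll 10 individuals allowing for 18% attrition (n=2 individuals not completing the study) for a total of 8 participants". Section 4.8 repeats the purpose: "We are only collecting 8-10 participants as a proof-of-concept study for pilot data to support grant applications for larger clinical trials".

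Neither 4.6 nor the synopsis names Hedges' g or any other small-sample correction. The documents give no pre-post correlation and do not say how the interval for d will be computed.

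**The concern.** Cohen's d divides a mean difference by an SD estimated from the same few people. The reciprocal of a sample SD is, on average, larger than the reciprocal of the true SD, so d lies further from zero on average than the effect it estimates. In large samples this can be ignored. With 8 people the SD rests on 7 to 14 degrees of freedom, and it cannot.

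The bias is present whichever SD is used as the standardiser (pooled, baseline or SD of change), so it is separate from the question of how the pairing is handled. The Aim 2 correlations are not affected.

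The effect size is the main product of this pilot and is meant to be quoted in grant proposals. A known directional error in it should be removed when removal needs no new data.

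**Working it through.** **Inputs from the documents.** One arm, measured twice (2.1); 10 enrolled and 8 completing, with d = 1.2 at 80% power and two-sided alpha 0.05 (4.7); pooled Cohen's d (4.6 and synopsis).

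**Assumed.** Normal data, equal pre and post SDs, and a pre-post correlation rho from 0 to 0.9.

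**The plan's own figure.** For a paired t-test with df = n - 1 and noncentrality d*sqrt(n), power at d = 1.2 is 75.4% for n = 7 and 82.8% for n = 8. So 8 is the smallest n that reaches 80%. The effect detectable with exactly 80% power at n = 8 is 1.16, which rounds to 1.2. The stated figure reproduces. It does so with d standardised by the SD of the change, which is not the pooled SD of 4.6. Below, 1.2 serves only as an example of a true effect on the pooled scale.

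**Bias formula.** For normal data the mean difference is independent of the pooled SD, so

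E[d]/delta = sqrt(df/2) * Gamma((df-1)/2) / Gamma(df/2) = 1/J.

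For a pooled SD from paired data the effective df is approximately 2(n-1)/(1+rho^2). At n = 8 that runs from 14 (rho = 0) down to 7 (rho approaching 1).

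- df = 14: 1/J = 1.058, J = 0.945
- df = 7: 1/J = 1.126, J = 0.888

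**Simulation of pooled d** (300,000 paired normal datasets per setting), mean of d divided by the true d:

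| rho | n = 8 | n = 10 |
|---|---|---|
| 0 | 1.058 | 1.044 |
| 0.5 | 1.071 | 1.055 |
| 0.8 | 1.095 | 1.073 |
| 0.9 | 1.109 | 1.083 |
| limit, rho to 1 (exact) | 1.126 | 1.094 |

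At n = 8, a true d of 1.2 is therefore reported on average as 1.27 (rho 0), 1.29 (rho 0.5) or 1.33 (rho 0.9), a bias of 0.07 to 0.13. If the SD of the change were the standardiser, the bias would be 12.6% at n = 8 and 9.4% at n = 10, whatever rho is.

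**Against sampling error.** At n = 8 and true d = 1.2, the SD of d is 0.60 (rho 0), 0.49 (rho 0.5) and 0.43 (rho 0.9). Squared bias is about 1-9% of mean squared error.

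**Does the correction work?** Take J = 1 - 3/(4*df - 1) with df = 2(n-1)/(1+r^2), where r is the correlation observed in the sample. At r = 0 and n = 8, df = 14 and J = 1 - 3/55 = 0.945. At r = 0.9, df = 14/1.81 = 7.73 and J = 1 - 3/29.9 = 0.900. In simulation the mean of g = J*d was 0.99-1.00 of the true value at n = 8 and n = 10, for true d of 0.5 and 1.2. Total error fell as well: at n = 8 and true d = 1.2, root mean squared error went from 0.60 to 0.56 (rho 0) and from 0.45 to 0.39 (rho 0.9).

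**The case against.** The strongest reply is that the bias is small beside the noise, and that the plan already shows the noise by committing to confidence intervals and by explaining its emphasis on estimation by the small sample. The bias is also a property of the average. At n = 8 and a true d of 1.2, a single pilot's d exceeds the truth in only 51-56% of datasets, and the median overstatement is about 2-4%. Corrected g exceeds the truth in 42-46%. All of this stands and limits the weight of the point. It does not justify keeping d, because the correction removes the mean bias and lowers total error too.

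Three further limits also stand. The lack of a correction is inferred from silence, although an analyst following 4.6 as written would report plain d. The 6-11% range rests on an assumed correlation. The formulas assume normal data, whereas KOOS-QOL is bounded at 0-100 and capped at entry, so the percentages are only approximate for Aim 3. The correction is itself an approximation that uses an r estimated from 8 people, although it performed well in the check.

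A reader might infer more than the documents support:

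- *Every T1rho region and KOOS-QOL will look better than it is.* This does not follow. The bias multiplies the true effect: it is nil when there is no effect, it makes a worsening look worse, and it holds on average rather than for each estimate.
- *The next trial will be 11-19% too small*, from 1 - 1/1.06^2 and 1 - 1/1.11^2. The documents speak of grant proposals and never say that the observed d will be entered into a sample-size formula. The successors they describe are randomised, and a single-arm pre-post d is not the between-group effect that such a trial is powered on.
- *The lower confidence limit should be used for planning.* At n = 8 and a true d of 0.5, the paired lower limit is at or below zero in 86% (rho 0) to 23% (rho 0.9) of datasets. At a true d of 1.2 with rho 0 it is so in 46%. No sample size can be computed from such a limit.

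**Conclusion.** The point holds as a modest, cheap improvement. With uncorrected pooled d as the main pre-post estimate, the average bias away from zero is about 6-11% at n = 8 and 4-8% at n = 10, given normal data, a non-zero true effect and a pre-post correlation of 0 to 0.9. The limit at n = 8 is 12.6%. Sampling error is several times larger than the bias, so the correction sharpens the estimate without changing what a study of this size can show. The documents support no claim about the size of a later trial or the direction of any particular result.

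**What to change.** In section 4.6 and in the synopsis, replace pooled Cohen's d with Hedges' g for each pre-post outcome: d multiplied by J = 1 - 3/(4*df - 1), with df = 2(n-1)/(1+r^2), n the number of pairs analysed and r the observed pre-post correlation. Give the 95% confidence interval on the same scale. State the SD and df used, and say that g with its interval, not uncorrected d, is what goes into grant proposals.

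The cost is one sentence in each place and one multiplication per outcome, on data already being collected. The downside is that reported effect sizes become about 5-11% smaller at n = 8 (J from about 0.945 to 0.889).

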### 1.4 Primary Objective

Aim 1. Determine the change in magnetic resonance imaging (MRI) markers of proteoglycan density after 8-weeks of daily step promotion. Hypothesis: Exposure to individualized physical activity promotion will decrease T1rho relaxation times (i.e. improve in vivo estimates of proteoglycan density) from pretest to posttest.

Aim 2. Determine the associations between change in free-living mechanical loading and change in MRI markers of proteoglycan density after 8-weeks of daily step promotion. Hypothesis: Greater increases in steps per day will be associated with greater decreases in T1rho relaxation times (i.e. improve in vivo estimates of proteoglycan density) from pretest to posttest.

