## 2 INVESTIGATIONAL PLAN (brief overview)

### 2.1 Study Design

Type of design: Single-arm pre-test post-test clinical trial

- Screening Visit: The initial visit will include initial screening (i.e. screening question and fill out KOOS-QOL subscale), enrollment, walking biomechanics assessment, and instructional use of actigraph physical activity monitor which will be worn for 7 days during all waking hours.
- Baseline: The second visit will include Fitbit and smartphone initialization with MSU Researcher, collection of patient reported outcomes and MRI scan of their knee. Participants will wear the fitbit monitor on their non-dominant wrist for 2 weeks during all waking hours in free-living settings in preparation for the intervention.
- Intervention/Treatment: Between the second and third visit, participants will receive daily SMS message with daily step count goals on their smart phone for 8 weeks. The daily step goal is based

on an adaptive step goal paradigm in which their daily goal is based on the top 60th percentile of steps over the last 10 days.

- Follow up: The third visit will include the completion of surveys, returning the fitbit monitor, instructional use of the actigraph monitor for second wear period over 7 days, and MRI.

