### **3.4 Follow-up procedures**

After the intervention, participants will be outfitted at the laboratory with the research-grade actigraph accelerometer to monitor daily during free-living settings for 7 days and fill out the surveys (KOOS). The actigraph will be secured on a belt and placed on the right hip. Participants will be instructed to wear the device for 7 days (removed for water activity and sleep). Participants will also undergo another MRI of the surgical limb at the Biomedical Imaging Research Center.

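### Aim 1 is a within-person change in one knee, but 4.6 summarises it only by a pooled-SD Cohen's d with an unnamed 95% CI; the mean paired change and a CI that uses the pairing should be specified

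*Combined protocol and SAP*

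**What the plan says.** The design is one arm measured twice: "Type of design: Single-arm pre-test post-test clinical trial" (2.1). Aim 1 in 1.4 is to "Determine the change in magnetic resonance imaging (MRI) markers of proteoglycan density after 8-weeks of daily step promotion". The scan is repeated on the same knee: "Participants will also undergo another MRI of the surgical limb at the Biomedical Imaging Research Center" (3.4). Section 4.4 lists the regional pre and post T1rho values as primary endpoints 1 to 8 and the regional T1rho changes as endpoints 10 to 13.

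For the before/after comparison, 4.6 states that "Pretest and posttest outcomes will be analyzed with pooled Cohen's" d, giving "effect sizes and corresponding 95% confidence intervals to determine the magnitude of outcome differences between time points". The Protocol Synopsis (Statistical And Analytic Plan) has the same content. Neither place gives a formula for the interval, mentions the pre/post correlation, or plans a mean change in ms with its interval. The only analysis that 4.6 describes for change scores is the Aim 2 correlation, and there the interval method is named (Fisher's transformation).

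On purpose, 4.6 says "we will emphasize estimation of effect sizes rather than formal inferential statistical hypothesis testing for future grant proposals". On size, 4.7 says "With 8 ACLR individuals at each time point, we will be powered (80% power, two-tailed alpha level of 0.05", for a time effect of d=1.2. It names neither the test nor the denominator of d.

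**The concern.** A pooled-SD d is computed from the two means and the two SDs, and the interval most often attached to it is the one for two independent groups. That interval takes no account of the correlation between a person's two scans. When the correlation is moderate or high, the change is estimated more precisely than the interval shows.

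The study exists to supply effect-size estimates for later grant proposals, and no planned test would supply a paired result alongside d. Two quantities needed to size a later paired or baseline-adjusted trial, the SD of change and the pre/post correlation, are not among the planned outputs. A reader also cannot tell whether the d to be reported is on the same scale as the d=1.2 for which the study was sized.

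**Working it through.** **Inputs from the documents.** Analysed n=8, d=1.2, 80% power, two-sided alpha 0.05 (4.7); pooled d with a 95% CI (4.6, synopsis). **Assumed, because the documents do not give them:** pre/post correlation rho from 0 to 0.9, equal pre and post SDs, bivariate normal data.

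**Step 1: the plan's own figure.** Noncentral t, two-sided 0.05.
- As d_z = mean change / SD of change in a paired t-test (df=7): power 82.8% at n=8 and 75.4% at n=7, so 8 is the smallest n that reaches 80%. The detectable d_z at 80% power is 1.156, which rounds to 1.2.
- As an independent-groups d with 8 per time point: 60.8%; 80% would need 12 per time point.
- As a pooled d in a paired t-test, d_z = 1.2/sqrt(2(1-rho)). At rho 0.5 this is 1.2/sqrt(1) = 1.2. Power reaches 80% at rho of about 0.46.

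The stated n and power therefore fit a paired calculation.

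**Step 2: the two scales of d.** With equal SDs, pooled d = d_z × sqrt(2(1-rho)). A d_z of 1.2 equals a pooled d of 1.42 at rho 0.3, 1.20 at 0.5, 0.93 at 0.7 and 0.76 at 0.8. The scales agree only at rho=0.5.

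**Step 3: the interval for pooled d.** Two candidate standard errors, each used with z=1.96:
- Independent groups: SE² = 2/n + d²/(4n). At d=1.2 and n=8: 0.25 + 1.44/32 = 0.295, so SE = 0.543 and the interval is 0.14 to 2.26.
- Correlation-adjusted: SE² = d²(s1⁴ + s2⁴ + 2r²s1²s2²)/(8(n-1)sp⁴) + s_change²/((n-1)sp²), where s1 and s2 are the pre and post SDs, sp² = (s1²+s2²)/2, s_change is the SD of change and r is the observed correlation.

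Simulation, 400,000 trials per rho, n=8, true pooled d held at 1.2:

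| Assumed rho | Coverage, independent-groups CI | Mean width relative to adjusted CI | Power of paired t-test if pooled d=1.2 |
|---|---|---|---|
| 0 | 94.5% | 0.92 | 54.3% |
| 0.3 | 96.9% | 1.04 | 69.3% |
| 0.5 | 98.0% | 1.14 | 82.8% |
| 0.7 | 98.4% | 1.27 | 96.2% |
| 0.8 | 98.4% | 1.36 | 99.5% |

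The adjusted interval covers 95.2 to 95.5% over the rho values simulated. The paired-t interval for the mean change covers 95.0% at every rho.

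**Step 4: sensitivity.** The width ratio depends on the formula. A large-sample version of the adjusted SE, with n instead of n-1 in the second term, evaluated at an observed d of 1.2, gives an adjusted width of 1.71 at rho 0.5 and 1.44 at rho 0.8, against 2.13 unadjusted: ratios of 2.13/1.71 = 1.25 and 2.13/1.44 = 1.48. Holding d_z rather than pooled d at 1.2 gives 1.60 at rho 0.8, but there the pooled d has fallen to 0.76, so part of that figure reflects a smaller effect.

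**The case against.** The strongest reply is that the plan does not choose a wrong interval; it leaves the interval unnamed. The word pooled fixes the denominator of d, and a pooled d can carry an interval that uses the correlation. This stands. A reader might infer that the two time points will be treated as independent groups, but nothing in 4.6 or the synopsis says so.

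Second, the pairing is not overlooked. Endpoints 10 to 13 are within-person changes, Aim 2 analyses changes, and the synopsis sentence itself speaks of changes in the MRI measures. This also stands, and it limits the point to the Aim 1 summary, for which no interval method follows from those passages.

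Third, an error here would be conservative. Coverage is nominal or above, the point estimate does not move, and no decision rule depends on the interval. This is true. The cost is lost precision, not a false claim of benefit.

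Fourth, a reader might infer from the 60.8% figure that the study is too small. The documents do not support that: in a single-arm study with a time effect, the paired reading is the natural one, and it reproduces n=8. What is left in 4.7 is a missing label.

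**Conclusion.** The point holds as a gap in specification with a clearly better method available, not as a demonstrated analysis error. Aim 1 is a paired comparison whose only stated summary is a pooled d with an unnamed interval. If the independent-groups interval were used, then at n=8 and a true pooled d of 1.2 it would differ little from the adjusted one for rho 0 to 0.3. At rho 0.5 to 0.8 it would be about 1.14 to 1.36 times as wide as needed, with about 98% coverage. That size rests on the assumed interval, the assumed rho and equal SDs, and varies somewhat with the SE formula.

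Section 4.7 needs clarification only: its n and power are consistent with a paired t-test, but its d equals the d of 4.6 only at rho=0.5 with equal SDs.

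**What to change.** In 4.6 and the synopsis, for each T1rho region and for KOOS-QOL, report the mean within-person change (ms or points) with a paired-t 95% CI on n-1 degrees of freedom, the SD of change and the pre/post correlation. This interval needs no assumption about the correlation. If pooled d is kept, define its denominator and name an interval that includes the observed correlation, for example the adjusted SE in step 3.

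In 4.7, add one sentence stating which d the 1.2 is, the test assumed, and any pre/post correlation assumed.

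The cost is SAP wording and a few lines of code. No new data are needed and N does not change.

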#### 4.7 Sample Size and Power

We will enroll 10 individuals allowing for 18% attrition (n=2 individuals not completing the study) for a total of 8 participants. With 8 ACLR individuals at each time point, we will be powered (80% power, two-tailed alpha level of 0.05) to detect a strong time effect in proteoglycan density ( $d=1.2$ ) and strong correlation ( $r=0.77$ ) between change in steps and change in proteoglycan density.

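### Eight completers give about 69% power, not 80%, for r = 0.77 under the planned Pearson/Fisher analysis; 80% power needs a correlation of about 0.82

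*Combined protocol and SAP*

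**What the plan says.** Section 4.7 (Sample Size and Power) sets the numbers: "We will enroll 10 individuals allowing for 18% attrition (n=2 individuals not completing the study) for a total of 8 participants". It then gives one power statement, at "80% power, two-tailed alpha level of 0.05", covering two targets. One is a pre-post effect of d = 1.2; the sentence then goes on to the second, "and strong correlation ( $r=0.77$ ) between change in steps and change in proteoglycan density". The claim is made for the completers ("With 8 ACLR individuals at each time point"). No power model or software is named.

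Section 4.6 (Statistical Methods) fixes the analysis of the association. It is a bivariate Pearson analysis, in which "correlation coefficients and 95% confidence intervals will be constructed using Fisher's transformations to estimate the strength of the associations". The same section puts estimation ahead of formal testing.

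The association between change in steps and change in T1rho is Aim 2, listed under the Primary Objective. Section 4.4 lists change in daily steps as an endpoint, taken from 7-day monitor wear before and after the intervention. Section 3.3 sets each day's goal from the participant's own preceding 10 days of steps.

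**The concern.** A power figure for a correlation depends on whether the predictor's values are set by design or observed. Here they are observed. The goals adapt to each person, and the change achieved is whatever the accelerometer records. Both variables are random, and the matching calculation uses the sampling distribution of r under a bivariate model. With only 8 pairs, that gives a clearly different answer from a fixed-predictor formula.

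Aim 2 is one of two primary aims, and section 4.7 holds its only power calculation. The results are meant to support grant applications for larger trials. A reader who believes that 0.77 was detectable with 80% power will give a null Aim 2 result too much weight against the hypothesis. A later trial that reuses the same method for this aim would overstate its power as well.

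**Working it through.** **Inputs, all from section 4.7:** n = 8 completers, two-sided alpha 0.05, correlation 0.77, claimed power 80%. The analysis, from section 4.6, is a Pearson correlation with a Fisher 95% interval. The sign of the correlation does not matter for a two-sided calculation.

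**1. Reproducing the plan's figure.** Treat the predictor as fixed and use a noncentral t with n − 2 = 6 degrees of freedom:

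- Noncentrality = √n · r/√(1 − r²) = √8 × 0.77/√(1 − 0.5929) = 2.828 × 1.207 = 3.41.
- Critical t = 2.447.
- Power = 81.0%. The correlation detectable at 80% is 0.766, which rounds to 0.77.

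So the figure comes from a recognised formula, but from one for a fixed predictor.

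**2. Critical value for the planned test.** |r| must exceed t/√(n − 2 + t²) = 2.447/√(6 + 5.99) = 0.707. The Fisher 95% interval excludes zero when |r| exceeds tanh(1.96/√5) = 0.705. The two criteria are almost the same.

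**3. Power with both variables random.** Under bivariate normality the density of r is

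f(r) = (n − 2) Γ(n − 1) (1 − ρ²)^((n−1)/2) (1 − r²)^((n−4)/2) / [√(2π) Γ(n − ½) (1 − ρr)^(n−3/2)] × ₂F₁(½, ½; n − ½; (1 + ρr)/2).

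Integrating it beyond the critical values at ρ = 0.77 gives:

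| Completers | Power, t test of r | Power, Fisher interval excludes 0 | Correlation for 80% power (t test) |
|---|---|---|---|
| 8 | 69.0% | 69.3% | 0.821 |
| 9 | 76.1% | 76.4% | 0.790 |
| 10 | 81.7% | 81.9% | 0.761 |

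Simulation of 1,000,000 bivariate-normal samples at n = 8 gave 69.0% and 69.3%.

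**4. Where the gap comes from.** With a random predictor, the quantity under the square root in the noncentrality is not the constant 8. It is a chi-square variable with n − 1 = 7 degrees of freedom, whose mean is 7. Replacing 8 by 7 in the fixed formula lowers power from 81.0% to 75.8%. Averaging over the chi-square variation lowers it further, to 69.0%.

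**5. Other conventions.**

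- Fisher normal approximation: atanh(0.77) × √5 − 1.96 = 1.020 × 2.236 − 1.96 = 0.32, so power is 62.6%. The correlation detectable at 80% is 0.849.
- Completers needed by that approximation: ((1.960 + 0.842)/1.020)² + 3 = 10.54, so 11.
- Fisher approximation with a bias term: 67.2%. With a t-based critical r: 66.8%.
- A one-sided exact test at 0.05 gives 80.5%, but section 4.7 says two-tailed.

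Every two-sided method that treats both variables as random gives 63% to 69%.

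**6. Precision at an observed r = 0.77, n = 8.** The interval is tanh(1.020 ± 1.96/√5) = tanh(1.020 ± 0.877), which is 0.14 to 0.96.

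**7. The companion figure.** For a two-sided paired t test with 8 pairs, d = 1.2 gives 82.8% power, and the 80% detectable d is 1.16. That part of the statement holds, so the discrepancy is confined to the correlation.

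**The case against.** The strongest reply is that the figure is not an arithmetic slip. It reproduces from a standard formula, and section 4.7 names no model that it contradicts. That is right as a description of the source: the fault is a mismatch between the power model and the planned analysis. It does not rescue the claim, because the fixed-predictor model describes neither the analysis in section 4.6 nor a step change that is observed.

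A second reply is that little hangs on the 80%. This is a pilot, section 4.6 stresses estimation, section 4.8 gives a proof-of-concept rationale for 8 to 10 participants, and no decision rule uses 0.77. Every correlation will also be reported with an interval that shows its imprecision. This stands, and it limits the practical weight. Even so, section 4.7 makes an unqualified power claim, and it should be true of the analysis planned.

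A third reply is that section 4.7 counts on losing 2 of 10, whereas Aim 4 hypothesises at least 90% retention. Nine completers would give 76% and ten 82%. Also true, but section 4.7 makes its claim at 8, and even 9 falls short of 80%.

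Last, 0.82 rests on bivariate normality, which the documents do not state. That is fair, and the restated sentence should name the assumption. The cruder Fisher approximation is less favourable to the plan.

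**Conclusion.** The concern holds: the power statement for the correlation is wrong as written. For a two-sided 5% test of a Pearson correlation between two measured changes, 8 completers give about 69% power at 0.77. That is 11 points below the stated 80%. The correlation detectable at 80% is about 0.82, and reaching 80% at 0.77 takes 10 completers, which is the whole planned enrolment with no loss. Power here means the chance that the 95% interval excludes zero.

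The 69% and 0.82 assume bivariate normality. The size of the discrepancy depends on that, but none of the two-sided random-predictor calculations reaches 80%. The design and the planned analysis are not in question; the stated property is.

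**What to change.** Replace the correlation part of the power statement in section 4.7 with text such as:

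> With 8 completers, a two-sided 5% test of a Pearson correlation (bivariate normal model) has 80% power for an absolute correlation of at least 0.82; power at 0.77 is about 69%. If 0.77 is observed in 8 participants, the Fisher 95% interval is 0.14 to 0.96.

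The second sentence suits a plan that puts estimation first and that now gives no expected precision. The values for 9 and 10 completers (76% and 82% at 0.77) could be added, since retention may be better than assumed. The d = 1.2 figure needs no change on this account.

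The cost is one or two sentences, with no added participants and no change to procedures or analysis. The only loss is a slightly less favourable figure.
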